2.2.2 Dose Rationale

Enzalutamide given at 160 mg/day has been approved by the FDA and EMA for use in men with mCRPC. Pharmacokinetics and tolerability of enzalutamide in men and women are similar and there is no clinically meaningful difference in pharmacokinetics between subjects with mild, moderate or severe hepatic impairment (Child-Pugh Class A, B and C, respectively) versus healthy volunteers after a single 160 mg dose of enzalutamide. Safety will be monitored on an ongoing basis. The first review of unblinded data will occur after 21 randomized subjects have been treated for 28 days or discontinued from the study (whichever occurs first). If warranted, a dose adjustment can be made based on the safety data review.

2.3 Endpoints

2.3.1 Primary Endpoints

The primary efficacy variable is OS. OS is defined as the time from the date of randomization until date of death from any cause.

2.3.2 Secondary Endpoints

Safety Endpoints:

The safety of enzalutamide will be assessed on an ongoing basis by evaluation of AEs/serious AEs (SAEs), clinical safety laboratory tests, vital signs and other safety measures.

Pharmacokinetic Endpoints:

Predose plasma concentrations of enzalutamide and N-desmethyl enzalutamide will be analyzed.

Efficacy Endpoints:

- PFS, defined as the time from the date of randomization until the date of documented radiographic disease progression according to Response Evaluation Criteria in Solid Tumors (RECIST) 1.1 or death from any cause on study, whichever occurs first as assessed by the Investigator.

2.3.3 Exploratory Endpoints

Term	Percentage
GMOs	95
Organic	90
Natural	85
Artificial	75

3 STUDY POPULATION

3.1 Selection of Study Population

The study population will include male and female subjects with advanced (unresectable and/or metastatic) HCC with Barcelona Clinic Liver Cancer [BCLC] stage B or C of any etiology who have progressed on or were intolerant to sorafenib or other anti-VEGF therapy in the advanced setting and are not amenable to local therapies or any curative treatments. Subjects may have received 1 line of systemic therapy before or after sorafenib/anti-VEGF treatment.

3.2 Inclusion Criteria

Subject is eligible for the study if all of the following apply:

1. Subject has consented and signed an Institutional Review Board (IRB)/Independent Ethics Committee (IEC) approved written Informed Consent and privacy language as per national regulations (e.g., Health Insurance Portability and Accountability Act [HIPAA] for U.S. sites) prior to any study-related procedures (including withdrawal of prohibited medication, if applicable).

2. Subject is \geq 18 years of age or is considered an adult according to local regulation at the time of signing informed consent.
3. Subject has a documented diagnosis of advanced HCC of any etiology.
4. Subject has BCLC stage B or C.
5. Subject's lesions are not amenable to local therapies which may be beneficial, such as TACE, radiofrequency ablation, radiotherapy, etc., and the subject is not a candidate for any curative treatments such as resection or liver transplant.
6. Subject has hepatic function status of Child-Pugh Class A at Screening.
7. Subject has received prior systemic treatment for HCC with sorafenib or other anti-VEGF therapy and had confirmed disease progression or had discontinued treatment due to a drug-related toxicity. Subjects may have received 1 line of systemic therapy before or after sorafenib/anti-VEGF treatment
8. Subject has adequately recovered from toxicities due to prior HCC therapy to \leq grade 1.
9. Subject has an ECOG performance status \leq 1 at Screening and on Day 1.
10. Subject has available formalin-fixed, paraffin-embedded tumor specimen with adequate viable tumor cells in a tissue block or unstained serial slides accompanied by an associated pathology report prior to enrollment. Archival or fresh biopsy tissue is required.
11. Subject has an estimated life expectancy of at least 3 months on Day 1, in the opinion of the Investigator.
12. Female subject is either:
 - Not of childbearing potential:
 - postmenopausal (defined as no spontaneous menses for at least 12 consecutive months prior to Screening with FSH $>$ 40 IU/L for women $<$ 55 years of age at Screening), or
 - documented surgically sterile or status posthysterectomy (at least 1 month prior to Screening).
 - Or, if of childbearing potential:
 - must have a negative urine pregnancy test at Screening and on Day 1 before the first dose of study drug is administered, and
 - must use 2 acceptable methods of birth control* if sexually active from Screening through 3 months after the last dose of study drug.
13. Sexually active male subject and his female partner who is of childbearing potential must use 2 acceptable methods of birth control* from Screening through 3 months after the last dose of study drug.

*Two acceptable methods of birth control are as follows:

- Condom (barrier method of contraception);
AND
- One of the following is required:
 - Placement of an intrauterine device (IUD) or intrauterine system (IUS) by the female subject or female partner of a male subject;
 - Additional barrier method: contraceptive sponge or occlusive cap (diaphragm or cervical/vault caps) with spermicidal foam/gel/film/cream/suppository by the female subject or female partner of a male subject.
 - For male subject or male partner of female subject, vasectomy or other procedure resulting in infertility (e.g., bilateral orchietomy) performed at least 6 months before Screening.
 - Tubal ligation in the female partner of a male subject performed at least 6 months before Screening.
 - Established and ongoing use of oral, injected, or implanted hormonal contraceptive by female partner of a male subject.

14. Female subject must not be breastfeeding at Screening or during the study period and for 3 months after final study drug administration.
15. Subject must agree not to donate sperm or ova from first dose of study drug through 3 months after the last dose of study drug.
16. Throughout the study, male subject must use a condom if having sex with a pregnant woman.
17. Subject must be able to swallow study drug and comply with study requirements.
18. Subject agrees not to participate in another interventional study while on treatment.

Waivers to the inclusion criteria will **NOT** be allowed.

3.3 Exclusion Criteria

Subject will be excluded from participation if any of the following apply:

1. Subject has a severe concurrent disease, infection or comorbidity that, in the judgment of the Investigator, would make the subject inappropriate for enrollment.
2. Subject has fibrolamellar variant of HCC.
3. Subject has status of Child-Pugh Class B or C at Screening.
4. Subject has a history of organ allograft including liver transplant.
5. Subject has uncontrolled symptomatic ascites.
6. Subject has known or suspected brain metastasis or active leptomeningeal disease.

7. Subject has a history of a non-HCC malignancy with the following exceptions:
 - The subject with a previous history of a noninvasive carcinoma is eligible if in the opinion of the Investigator he/she has had successful curative treatment any time prior to Screening and requires no further therapy for the malignancy.
 - For all other malignancies, the subject is eligible if he/she has undergone potentially curative therapy and has been considered disease free for at least 3 years prior to Screening.
8. Subject has inadequate marrow, hepatic, and/or renal function at the Screening Visit defined as:
 - Absolute neutrophil count $< 1.5 \times 10^9/L$ ($< 1500 \text{ cells/mm}^3$)
 - Platelet count $< 50 \times 10^9/L$ ($< 50,000 \text{ cells/mm}^3$)
 - Hemoglobin $< 8.5 \text{ g/dL}$ ($< 5.3 \text{ mmol/L}$)
 - INR > 1.7
 - Albumin $< 2.8 \text{ g/dL}$ ($< 28 \text{ g/L}$)
 - Total Bilirubin (TBL) $> 2 \times \text{ULN}$
 - AST or ALT $> 5 \times \text{ULN}$
 - Creatinine $> 1.5 \times \text{ULN}$

Note: Transfusions/infusions to meet eligibility criteria are not allowed but if in the opinion of the Principal Investigator, it is beneficial, the patient may be rescreened after receiving one of these procedures.

9. Subject has a history of seizure or any condition that may predispose to seizure (e.g., prior cortical stroke, significant brain trauma, encephalopathy within 3 months of Day 1).
10. Subject has a history of bleeding esophageal varices within 3 months before the Day 1 visit.
11. Subject has a history of loss of consciousness or transient ischemic attack within 12 months before the Day 1 visit.
12. Subject has clinically significant cardiovascular disease including:
 - Myocardial infarction within 6 months before the Day 1 visit.
 - Uncontrolled angina within 6 months before the Day 1 visit.
 - Congestive heart failure New York Heart Association (NYHA) Class III or IV or history of congestive heart failure NYHA Class III or IV in the past, **UNLESS** a Screening echocardiogram or multi-gated acquisition scan performed within 3 months before the Day 1 visit reveals a left ventricular ejection fraction that is $\geq 45\%$.
 - History of clinically significant ventricular arrhythmias (e.g., ventricular tachycardia, ventricular fibrillation, Torsade de Pointes).
 - History of Mobitz II second degree or third degree heart block without a permanent pacemaker in place.
 - Hypotension as indicated by systolic blood pressure $< 86 \text{ mmHg}$ on 2 consecutive measurements at the Screening visit.

- Bradycardia (in the presence of known cardiovascular disease) as indicated by a heart rate of < 50 beats per minute on the Screening ECG recording.
- Uncontrolled hypertension as indicated by systolic blood pressure > 170 mmHg or diastolic blood pressure > 105 mmHg on 2 consecutive measurements at the Screening visit.

13. Subject has a gastrointestinal disorder affecting absorption.
14. Subject had previous local therapy (e.g., surgery, radiation therapy, hepatic arterial therapy, chemoembolization, radiofrequency ablation, percutaneous ethanol injection or cryoablation) within 14 days prior to Day 1, has not recovered from toxicities from prior local therapy or may require major surgical procedure during the course of the study.
15. Subject has received chemotherapy, immunotherapy or any other systemic anticancer therapy (including sorafenib) or any investigational drug within 14 days prior to the Day 1 visit.
16. Subject has received an agent that either blocks androgen synthesis or targets the AR (e.g., abiraterone acetate, bicalutamide, enzalutamide, ARN-509 or other investigational AR signaling modulator). The exception of spironolactone is allowed after Medical Monitor consultation.
17. Subject has used any of the following within 28 days before the Day 1 visit:
 - 5- α reductase inhibitors
 - Systemic androgens and estrogens (vaginal estrogen creams are allowed)
 - Herbal therapies, with an antitumor effect
18. Subject has a known history of positive test for Human Immunodeficiency Virus.
19. Subject has shown a hypersensitivity reaction to the active pharmaceutical ingredient or any of the enzalutamide capsule components, including caprylocaproyl polyoxylglycerides (Labrasol), butylated hydroxyanisole and butylated hydroxytoluene.
20. Subject has addictive/substance abuse problems.
21. Subject has any other condition or reason that, in the opinion of the Investigator interferes with the ability of the subject to participate in the trial, places the subject at undue risk or complicates the interpretation of safety data.

Waivers to the exclusion criteria will **NOT** be allowed.

4 TREATMENT(S)

4.1 Identification of Investigational Product(s)

4.1.1 Enzalutamide

Enzalutamide is an opaque white to off-white oblong liquid-filled soft gelatin capsule for oral administration. Each capsule contains 40 mg enzalutamide.

4.1.2 Placebo

The corresponding placebo is an opaque white to off-white oblong liquid-filled soft gelatin capsule for oral administration.

4.2 Packaging and Labeling

Both enzalutamide and the corresponding placebo are supplied by APGD. Enzalutamide and placebo will be packaged in high-density polyethylene bottles with child-resistant induction seal closure. There are 124 capsules per bottle. All medication used in this study will be prepared, packaged, and labeled under the responsibility of qualified staff at APGD- Astellas United States Technologies (AUST) or Sponsor's designee in accordance with APGD-AUST or Sponsor's designee Standard Operating Procedures (SOPs), Good Manufacturing Practice (GMP) guidelines, ICH Good Clinical Practice (GCP) guidelines, and applicable local laws/regulations.

Each bottle will bear a label conforming to regulatory guidelines, GMP and local laws and regulations which identifies the contents as investigational drug.

A qualified person of Astellas Pharma Europe B.V. (APEBV) or Sponsor's designee will perform the final release of the medication according to Directive 2003/94/EC annex 13.

4.3 Study Drug Handling

Enzalutamide and the corresponding placebo will be stored in a secure location with limited access at 20°C to 25°C (68°F to 77°F) with excursions permitted to 15°C to 30°C (59°F to 86°F). Subjects will be instructed to store study drug at room temperature and out of the reach of children.

Current ICH GCP Guidelines require the Investigator to ensure that study drug deliveries from the Sponsor are received by the Investigator/or designee (e.g., pharmacist), and:

- That such deliveries are recorded,
- That study drug is handled and stored according to labeled storage conditions,
- That study drug with appropriate expiry/retest and is only dispensed to study subjects in accordance with the protocol, and
- That any unused study drug is returned to the Sponsor.

Drug inventory and accountability records for the study drugs will be kept by the Investigator/ or designee. Study drug accountability throughout the study must be documented and reconciled. The following guidelines are therefore pertinent:

- The Investigator agrees not to supply study drugs to any persons except the eligible subjects in this study in accordance with the protocol.
- The Investigator or designee will keep the study drugs in a pharmacy or other locked and secure storage facility under controlled storage conditions, accessible only to those authorized by the Investigator to dispense these test drugs.
- A study drug inventory will be maintained by the Investigator or designee. The inventory will include details of material received and a clear record of when they were dispensed and to which subject.
- At the conclusion or termination of this study, the Investigator or designee agrees to conduct a final drug supply inventory and to record the results of this inventory on the Drug Accountability Record. It must be possible to reconcile delivery records with those of used and/or returned medication. Any discrepancies must be accounted for and documented. Appropriate forms of deliveries and returns must be signed by the site staff delegated this responsibility.
- The site must return study drug to the Sponsor or designee at the end of the study or upon expiration.

4.4 Blinding

This is a double-blind study. Subjects will be randomized to receive enzalutamide or placebo in a double-blind fashion such that the Investigator, Sponsor's study management team, clinical staff nor the subject will know which agent is being administered. The randomization number will be assigned based on information obtained from the Interactive Response Technology (IRT).

4.4.1 Confirmation of the Indistinguishability of the Study Drugs

The control for this blinded study will be the placebo capsules that appear identical to the enzalutamide capsules. Study drug will be dispensed in the same manner regardless of assigned treatment arm. Subjects will ingest the same number of capsules throughout the study.

4.4.2 Retention of the Assignment Schedule and Procedures for Treatment Code Breaking

The randomization list and study medication blind will be maintained by the IRT system.

The DSMB will be provided access to the treatment assignment for periodic review of the unblinded data as documented in the DSMB Charter.

4.4.3 Breaking the Treatment Code for Emergency

The treatment code for each randomized subject will be provided by the IRT in the event of a medical emergency requiring knowledge of the treatment assigned to the subject. The time, date, subject number and reason for obtaining any of these codes, and therefore breaking the blind, must be documented in the study file. They must only be requested by the Investigator or other persons designated as sub-Investigators. No subjects or other study personnel will be

made aware of the treatment given to any subject unless a medical emergency necessitates such disclosure.

Unblinding of the study medication should only be considered for subject safety or when critical therapeutic decisions are contingent upon knowing the blinded study drug assignment. Any unblinding by the investigational staff must be reported immediately to the Sponsor and must include an explanation of why the study medication was unblinded. If possible, the Sponsor should be contacted prior to unblinding of the study medication.

4.4.4 Breaking the Treatment Code by the Sponsor

The Sponsor may break the treatment code for subjects who experience a Suspected Unexpected Serious Adverse Reaction (SUSAR), in order to determine if the individual case or a group of cases requires expedited regulatory reporting. Individual Emergency Codes will be provided to the limited staff who are responsible to break the codes for all SUSAR cases for reporting purposes.

4.5 Assignment and Allocation

Subjects will be entered into the IRT system at Screening and assigned a number. Subjects who meet inclusion/exclusion criteria will be stratified by geographic region (Asia versus other) and ECOG performance status (0 versus 1) and randomized in a 2:1 ratio to receive enzalutamide 160 mg/day or placebo on Day 1. Randomization will be performed via IRT. Prior to the initiation of the study treatment, the site staff will contact the IRT in order to determine the randomly assigned treatment. Specific procedures for randomization through the IRT are contained in the IRT procedures manual.

5 TREATMENTS AND EVALUATION

5.1 Dosing and Administration of Study Drug(s) and Other Medication(s)

5.1.1 Dose/Dose Regimen and Administration Period

Eligible subjects will receive enzalutamide 160 mg/day (4 x 40 mg capsules) or placebo until disease progression, unacceptable toxicity, or any other discontinuation criteria are met. Best supportive care will be given to all subjects in addition to study drug. Best supportive care may include medications and supportive measures deemed necessary per Investigator's discretion to palliate disease-related symptoms and improve quality of life. Subjects on strong CYP2C8 (e.g., gemfibrozil) inhibitor should start study drug at 80mg/day after consultation with the Medical Monitor, if coadministration cannot be avoided.

Study drug will be self-administered at home by the subject, except for visit days where pharmacokinetic samples are collected. On visit days with pharmacokinetic sampling, study drug will be administered in clinic after the pharmacokinetic sample is collected. Subjects will keep a diary to record the date and time of study drug dose on the 2 days before pharmacokinetic visit days.

Subjects should not make up missed or vomited doses; dosing should resume on the next calendar day unless otherwise instructed. For the purposes of this study, a “missed dose” is considered a dose not administered within 4 hours of the regular dosing time.

Subjects may take study drug with or without food. Subjects must swallow capsules whole. Study drug may not be chewed, dissolved or capsules opened.

5.1.2 Increase or Reduction in Dose of the Study Drug(s)

During the study, study drug treatment may be interrupted for individual subjects who experience a NCI CTCAE Grade ≥ 3 AE (except LFT AEs) that is attributed to the study drug and cannot be ameliorated with appropriate medical intervention. Study drug may be resumed at the original dose (160 mg/day) or at a reduced dose (120 mg/day or 80 mg/day), after discussion with and approval by the Medical Monitor. Treatment interruption for > 2 weeks must also be discussed with the Medical Monitor. The Sponsor may make a decision to change the dose based on recommendation from the DSMB’s safety review.

5.1.2.1 Dose Modification Plan for LFT Changes

Study drug dosing should be interrupted if a subject experiences clinically significant liver toxicity related to study drug (\geq Baseline + 4 x ULN to < 20 x ULN for AST and ALT; grade 3 TBL). Testing should be repeated at Investigator’s discretion but at a minimum weekly to ensure that the subject’s LFT’s are returning to acceptable levels. If the subject’s toxicity resolves within 14 days to either \leq grade 1 (if normal at baseline) or no more than 1 grade above baseline (but no higher than grade 2), study drug may be reintroduced at a dose of 120 mg/day in consultation with the Medical Monitor. If the toxicity has not resolved within 14 days (as defined by either \leq grade 1 or no more than 1 grade above screening but no higher than grade 2), then the Medical Monitor must be consulted to determine if further interruption is permitted.

If any drug-related liver toxicity requiring dose interruption recurs or develops despite the initial dose reduction to 120 mg/day, the LFT monitoring instructions above should be followed and the study drug may be reintroduced at a dose of 80 mg/day. If any drug-related liver toxicity recurs at the reduced dose of 80 mg/day, the study drug should be discontinued.

Study drug must be discontinued for subjects with study drug related grade 4 LFTs (AST, ALT and TBL).

Table 2 Dose Modification Table for Drug-Related Liver Toxicities

NCI CTCAE V4.03	Dose Interruption	Dose Reduction
Grade 1 (AST, ALT, TBL)	No Change	No Change
Grade 2 to < Baseline + 4 x ULN (AST and ALT)	No Change	No Change
Grade 2 (TBL)	No Change	No Change
≥ Baseline + 4 x ULN and below 20 x ULN (AST and ALT)	Hold until grade 1 or, if event was grade 1 or 2 at screening, until returns to grade 2 or lower. If it takes over 14 days to reduce toxicity to acceptable levels then the MM should be consulted	1st episode – reduce to 120 mg/ day 2nd episode – reduce to 80 mg/day 3rd episode – Discontinue treatment
Grade 3 (TBL)	Hold until grade 1 or, if event was grade 2 at screening, until returns to grade 2 or lower. If it takes over 14 days to reduce toxicity to acceptable levels then the MM should be consulted	1st episode – reduce to 120 mg/day 2nd episode – reduce to 80 mg/day 3rd episode – Discontinue treatment
Grade 4 (AST, ALT, TBL)	Discontinue Treatment	Discontinue Treatment

Abbreviations: ALT: alanine aminotransferase; AST: aspartate aminotransferase; NCI CTCAE: National Cancer Institute Common Toxicity Criteria for Adverse Events; TBL: total bilirubin; ULN: upper limit or normal

Note: For any Grade 3 or 4 hepatic toxicity that does not resolve within 14 days to CTCAE Grade \leq 1 (or CTCAE Grade \leq 2 if liver infiltration with tumor present), an abdominal CT scan should be performed to assess if the event is related to disease progression. Subjects with a history of viral hepatitis and an ALT or AST \geq Baseline + 4 x ULN while on treatment should have a hepatitis B and C viral loads performed per institutional guidelines to check for possible reactivation.

For Grade 4 LFTs (AST, ALT, TBL), increases related to the underlying disease or other nonstudy drug related causes, the Investigator in consultation with the Medical Monitor may consider holding study drug until values return to baseline or lower.

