5.1.3 Previous and Concomitant Treatment (Medication and Nonmedication Therapy)

Medications taken within 14 days before the Screening visit and up to the 30-Day Follow-up visit will be documented on the appropriate case report form.

Prior and concomitant medications include all vitamins, herbal remedies, over the counter, and prescription medications.

Subject with viral etiology (HCV, HBV) should be on stable doses of antiviral therapy at the time of study entry, if the Investigator feels these are of benefit to the subject. The Investigator should consult with Medical Monitor if initiation of antiviral therapy is deemed necessary during the study.

Concomitant use of enzalutamide with drugs with a narrow therapeutic index that are metabolized by CYP3A4 (e.g., alfentanil, cyclosporine, dihydroergotamine, ergotamine, fentanyl, pimozide, quinidine, sirolimus, tacrolimus), CYP2C9 (e.g., phenytoin, warfarin) and CYP2C19 (e.g., S-mephenytoin) should be avoided if possible as enzalutamide may

decrease their exposure. If coadministration with warfarin cannot be avoided, additional INR monitoring should be conducted.

Coadministration of enzalutamide with strong CYP2C8 inhibitors should be avoided. If coadministration of enzalutamide with strong CYP2C8 inhibitors cannot be avoided, the enzalutamide dose should be reduced to 80 mg/day. If coadministration of the strong inhibitor is discontinued, the enzalutamide dose should be returned to the dose used before initiation of the strong CYP2C8 inhibitor.

Subject should avoid use of any herbal medications or dietary supplements including products containing *Hypericum perforatum* (e.g., St. John's wort).

The following medications or therapies are prohibited during the receipt of study drug:

- Medications, including herbal therapies, with an antitumor effect
- Any investigational agent
- AR antagonists (e.g., bicalutamide, flutamide, nilutamide), however, spironolactone initiation during the study is allowed after Medical Monitor consultation
- 5- α reductase inhibitors (e.g., finasteride, dutasteride)
- Systemic androgens and estrogens (vaginal estrogen creams are allowed)

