6 DISCONTINUATION

6.1 Discontinuation of Individual Subject(s)

A discontinuation is a subject who enrolled in the study and for whom study treatment is permanently discontinued for any reason.

The subject is free to withdraw from the study treatment and/or study for any reason and at any time without giving reason for doing so and without penalty or prejudice. The Investigator is also free to terminate a subject's involvement in the study at any time if the subject's clinical condition warrants it or for reasons of gross noncompliance.

If a subject is discontinued from the study with an ongoing AE or an unresolved laboratory result that is significantly outside of the reference range, the Investigator will attempt to provide follow-up until the condition stabilizes or no longer is clinically significant.

Discontinuation Criteria from Treatment for Individual Subjects:

- Evidence of symptomatic and radiographic disease progression per Investigator's assessment.
- Subject develops an unacceptable drug-related AE, based on the opinion of the Investigator and in consultation with the Medical Monitor
- Seizure of any grade.
- Subject's disease becomes amenable to local or curative treatments.
- Subject is lost to follow up despite reasonable efforts by the Investigator to locate the subject
- There is a significant protocol violation or non-compliance that occurs with a subject that compromises study objectives or subject safety.
- Female subject becomes pregnant
- Subject's death
- Increased liver function tests per discontinuation criteria in Section 5.1.2.1 Dose Modification Plan for LFT Changes

Discontinuation Criteria from Post-Treatment Follow Up for Individual Subjects:

- Subject withdraws consent for further study participation
- Subject is lost to follow up despite reasonable efforts by the Investigator to locate the subject
- Subject's death

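### The liver-toxicity dose rule assumes the subject is on 160 mg/day at the first episode; for a subject already on 120 or 80 mg/day it gives no reduction or no usable dose

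*Protocol*

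**What the plan says.** Protocol section 5.1.2.1 states the liver rule twice.

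- **Table 2**, in both the AST/ALT row and the grade 3 bilirubin row, goes by episode count: "1st episode – reduce to 120 mg/ day 2nd episode – reduce to 80 mg/day 3rd episode – Discontinue treatment".
- **The text** says that once the first toxicity has resolved, "study drug may be reintroduced at a dose of 120 mg/day in consultation with the Medical Monitor". Toxicity that "recurs or develops despite the initial dose reduction to 120 mg/day" may then be followed by a restart at 80 mg/day. Finally, "If any drug-related liver toxicity recurs at the reduced dose of 80 mg/day, the study drug should be discontinued". The Synopsis carries the same text.

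Neither statement is limited to subjects taking 160 mg/day. Other sections provide for lower doses before any liver event:

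- Section 5.1.2, after a drug-related non-liver AE of grade 3 or higher: "Study drug may be resumed at the original dose (160 mg/day) or at a reduced dose (120 mg/day or 80 mg/day"), with Medical Monitor approval.
- Section 5.1.1, where coadministration cannot be avoided: "Subjects on strong CYP2C8 (e.g., gemfibrozil) inhibitor should start study drug at 80mg/day", after Medical Monitor consultation.
- Section 5.1.3, during the study: "If coadministration of enzalutamide with strong CYP2C8 inhibitors cannot be avoided, the enzalutamide dose should be reduced to 80 mg/day".

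The rule still applies in the open-label period. Appendix 12.9 refers to Section 5.1 for dose modification and carries reduced doses over.

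**The concern.** A rule for dosing after liver toxicity should give a lower dose, or a stop, from every dose the protocol permits. Here the first step is a fixed figure, 120 mg/day, that takes no account of the dose at onset. Subjects who reached 120 or 80 mg/day by a route written into the protocol are therefore not properly covered.

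The patients have hepatocellular carcinoma and have just had a liver event attributed to study drug. Sites could restart such subjects at different doses. If Table 2 is followed to the letter, a subject on 120 mg/day resumes at the dose on which the toxicity occurred.

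**Working it through.** No figure in the plan needs reproducing; the check is to trace the rule from each permitted dose. Inputs are the doses 160, 120 and 80 mg/day (sections 5.1.1 to 5.1.3) and the first-episode step of 120 mg/day (Table 2 and the text of 5.1.2.1). The ratio is restart dose divided by dose at onset.

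| Dose at first liver episode | How the subject got there | Restart dose as written | Ratio | Change |
|---|---|---|---|---|
| 160 mg/day | planned dose | 120 mg/day | 120/160 = 0.75 | 25% lower |
| 120 mg/day | non-liver AE (5.1.2) | 120 mg/day | 120/120 = 1.00 | none |
| 80 mg/day | non-liver AE (5.1.2) or CYP2C8 inhibitor (5.1.1, 5.1.3) | 120 mg/day | 120/80 = 1.50 | 50% higher, so not a usable step |

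**Standard path.** From 160 mg/day, table and text both give 160 to 120 (25% lower), 120 to 80 (80/120 = 0.667, 33% lower), then stop. They agree.

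**First episode at 80 mg/day.** The 80 mg stopping sentence does not clearly help, because it covers toxicity that recurs and a first episode has not recurred. No dose below 80 mg/day is named. Table 2's instruction to reduce to 120 mg/day cannot be carried out from 80. The only restart dose the text gives for a first episode is 120 mg/day.

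**With a strong CYP2C8 inhibitor.** Protocol section 1.2.2.1 reports a 2.2-fold composite AUC with gemfibrozil and approximate dose proportionality at steady state. Assuming that factor holds for the inhibitor used:

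- 80 mg/day: 80 × 2.2 = 176 mg/day equivalent, and 176/160 = 1.10 times the planned dose.
- 120 mg/day: 120 × 2.2 = 264 mg/day equivalent, and 264/160 = 1.65 times the planned dose.

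This shows why the 80 mg limit in section 5.1.3 should hold through a liver restart.

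**The case against.** **Clinical oversight would catch this.** The text restart is permissive and made in consultation with the Medical Monitor. The Medical Monitor must also approve a non-liver reduction and be consulted on an 80 mg/day start, so would normally know of the lower dose. Table 2 says to reduce, which no one would take as an order to go up. Section 5.1.3 separately holds a subject on a strong CYP2C8 inhibitor at 80 mg/day, and nothing in 5.1.2.1 overrides it. All of this stands, and it makes an actual increase unlikely. But consultation supplies no dose, and in the Table 2 rows that set the dose steps the Medical Monitor is named only for holds beyond 14 days. None of it corrects the step from 120 to 120.

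**Table and text might be thought to contradict each other.** A reader might infer this in two cases. In the first, an initial liver episode occurs at 120 mg/day and "recurs or develops despite the initial dose reduction to 120 mg/day" is taken to point to 80. In the second, another liver episode occurs at 80 mg/day reached after a non-liver AE; Table 2 then says 80 and the text might say stop, which would matter because section 6.1 lists "Increased liver function tests per discontinuation criteria in Section 5.1.2.1 Dose Modification Plan for LFT Changes" as a reason to stop treatment. The documents do not establish either conflict. Each phrase directly follows the liver restart at that dose and most naturally means that liver reduction. Section 6.1 also allows stopping for an unacceptable drug-related AE, so stopping does not turn on this wording alone.

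**Reach is limited.** Coadministration with strong CYP2C8 inhibitors is to be avoided in the first place. Appendix 12.9 reports that the primary analysis is done, and only ongoing enzalutamide subjects may continue. This limits the importance of the error; the rule nevertheless remains in force for those subjects.

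**Conclusion.** The rule is wrong as written, to a minor degree, and only as a safety rule. The fixed first restart of 120 mg/day works from 160 mg/day, gives no reduction from 120, and gives no usable step from 80.

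This rests on two things visible in the Protocol: the lower doses are permitted before any liver event, and nothing limits Table 2 or the first-restart sentence to subjects on 160 mg/day. The number of subjects affected is not given and cannot be derived.

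A reader might infer that the protocol directs a dose increase after liver toxicity. That goes too far, given the permissive wording, the Medical Monitor's role and section 5.1.3. The primary overall survival analysis, its alpha and the sample size do not depend on this rule.

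**What to change.** Use one rule in Table 2, the text of 5.1.2.1 and the Synopsis:

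- After a drug-related liver toxicity requiring dose interruption, resume one level below the dose at onset: 160 to 120, or 120 to 80 mg/day.
- For a first liver episode at 80 mg/day, do not resume above 80 mg/day. Discontinue if a drug-related liver toxicity requiring dose interruption recurs at 80 mg/day.
- Do not exceed 80 mg/day while the subject takes a strong CYP2C8 inhibitor.
- If the inhibitor is stopped after a liver episode, any return to a higher dose under section 5.1.3 needs Medical Monitor approval and may not exceed 120 mg/day after one episode or 80 mg/day after two.

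The last item is needed because section 5.1.3 otherwise returns the subject to the dose used before the inhibitor. The standard path of 160, 120, 80, stop is unchanged.

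The sponsor's clinical team may prefer the stricter option of discontinuing at a first liver episode at 80 mg/day; that is a clinical decision to be written into the rule.

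The cost is a short amendment. Because it affects subject safety, section 8.3.3 requires written verification of IRB/IEC approval before it is implemented. No new data or subjects are needed.
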